5.1.8 Neurocognitive, Developmental and Quality of Life (QOL) Assessments

Neurocognitive, developmental and QOL assessments are presented in Section 14.5 (Appendix E) and will be performed at time points specified in the SOA. BSID-III and/or KABC-II, and BOT-2 Brief Form are administered to the subject. All other assessments are administered to the parent or caregiver.

The investigator or designee should use clinical judgement to decide whether subject hearing or vision problems may preclude developmental testing. Assessment of vision and hearing may be collected from medical history, parent report and/or based on evaluation during Screening physical exam.

Assessments to be performed will include the Vineland-II, BSID-III and/or KABC-II, BOT-2 Brief Form, CCC-2, CSHQ, SBRS, ZBI 12-item, and the SF-10. The Vineland-II, BSID-III or KABC-II and BOT-2 Brief Form should be administered face to face by appropriately qualified professionals. Assessments may be conducted over more than 1 day.

The selection of the appropriate neurocognitive test instrument administered to the child is normally dependent on the calendar age of the child. However, since MPS IIIB patients are likely to show delayed development, the choice of test instrument at the Screening visit will be based on a subject's Vineland-II age equivalent (developmental age) assessed using the survey interview form. The BSID-III will be administered to subjects with a mean Vineland-II age-equivalent of < 3 years 6 months, and the KABC-II, BOT-2 Brief Form, and CCC-2 will be administered to subjects with a Vineland-II age-equivalent of \geq 3 years 6 months.

During the initial administration of the BSID-III or KABC-II, BOT-2 Brief Form, and CCC-2 at Screening, if the test administrator determines that the chosen test instrument appears unfit for the subject, he/she may switch to the alternate test instrument. However, after the Screening visit, the KABC-II should be first attempted. If the subject appears to be failing the KABC-II, they

may revert to the BSID-III. If the subject passes the BSID-III, the KABC-II should be continued. See Sections 5.1.8.2 and 5.1.8.3 for details.

5.1.8.1 Vineland Adaptive Behavior Scales, Second Edition (Vineland-II)

The Vineland-II supports the diagnosis of cognitive and developmental disabilities in subjects from birth through age 90 years. The Vineland-II assesses a subject's abilities across 5 domains: communication, daily living skills, socialization, motor skills, and maladaptive behaviors. In this study, all sections except for the critical items in the Maladaptive Behavior domain will be used. Standardized scores, percentile ranks, and adaptive levels are provided for each domain, as well as for an adaptive behavior composite measure. Additionally, the Vineland-II allows for determination of V-scale scores, adaptive levels, and age equivalents for subdomains of each of the 5 adaptive behavior domains. Administration of the Vineland-II Survey Interview Form with the parent/caregiver takes approximately 20 to 60 minutes.

The Vineland overall adaptive behavior composite (mean domain age equivalent) will be calculated based on all age equivalent scores for the sub-domains under communication, daily living skills and socialization, both including and excluding motor skills. Maladaptive behavior is not included in this calculation. A developmental quotient (DQ) will also be calculated as: (age equivalent / calendar age) \times 100; DQ will also be calculated both including and excluding the motor domain.

5.1.8.2 Bayley Scales of Infant and Toddler Development, Third Edition (BSID-III)

The BSID-III has been validated for children aged less than 3.5 years and takes approximately 25 to 60 minutes to administer (Connolly 2012, *Pediatr Phys Ther*). The test is administered to the subject and was designed to identify young children with development delays. The BSID-III assesses developmental function across 5 domains: cognition; language (expressive and receptive); motor (fine and gross motor functioning); and social, emotional, and adaptive behavior.

In this study, cognition, language, and motor functioning will be assessed. The social, emotional, and adaptive behavior domains are not being used due to overlap with the Vineland scale. The mean domain age equivalent will be calculated based on all age equivalent scores for the sub-tests, and mean overall age equivalent will be calculated based on all domain age equivalent scores. A DQ will also be calculated as: (age equivalent / calendar age) \times 100.

Switching from BSID-III to the KABC-II

At the Screening visit, a child may perform better than expected based on the Vineland-II test. If the score on the first subdomain (cognition) is higher or equal to 79, the KABC-II should be used in combination with BOT-2 and CCC-2.

During future study visits, the KABC-II should be attempted first. If the subject appears to be failing the KABC-II, they may revert to the BSID-III. If the subject passes the BSID-III, the KABC-II should be continued at this visit when practical and subject compliance allows.

5.1.8.3 Kaufman Assessment Battery for Children, Second Edition (KABC-II)

The KABC-II has been validated for children aged 3 to 18 years and takes approximately 35 to 70 minutes to administer (Malda 2010, *Assessment*). The test is administered to the subject and was designed to identify strengths and weaknesses in cognitive ability and mental processing.

The KABC-II is comprised of 18 subtests, although not all subtests are required to be administered, and is typically used in conjunction with other cognitive or neuropsychological assessments.

Order of completion of the sub-tests by MPS IIIB Subjects

Children with MPS IIIB may not be able to complete all subtests, due to a limited attention span and behavioral problems. Therefore, only completion of the non-verbal index (NVI) battery, as appropriate for the developmental age of the child, is required to be completed. Other skills (language and motor skills) will be assessed by the CCC-2 and BOT-2 Brief Form, respectively. Priority should be given to the most informative domains, the required NVI tests and the BOT-2 Brief Form. The CCC-2 is completed by the parents. After completion of the NVI and BOT-2 Brief Form, the rater can complete the optional domains in order of importance, and thus, relevance. The NVI and BOT-2 Brief Form should be administered first. The optional domains include Sequential/Gsm, Simultaneous/Gv, Learning/Glr, Planning/Gf (only for developmental ages 7-18 years), and Knowledge/Gc.

Switching from KABC-II to the BSID-III

At the Screening visit, a child may perform poorer than expected on the KABC-II. In this case the BSID-III should be used. It is likely that these children will have started with the NVI subtests for children 3-5 years. The first tests for the NVI are Conceptual thinking and Face recognition. If the raw scores for both these first two tests are ≤ 5 then the KABC-II should be discontinued and the BSID-III should be used.

During future study visits, the KABC-II should be attempted first. If the subject appears to be failing the KABC-II, they may revert to the BSID-III. If the subject passes the BSID-III, the KABC-II should be continued at this visit when practical and subject compliance allows.

5.1.8.4 Bruininks-Oseretsky Test of Motor Proficiency, Second Edition, Brief Form (BOT-2 Brief Form)

The BOT-2 Brief Form is an individually administered test that uses engaging, goal-directed activities to measure a wide array of motor skills in children aged 4 through 21 years (Bruininks 2010, *NCS*). The BOT-2 Brief Form contains 12 items to assess fine motor precision, fine motor integration, manual dexterity, bilateral coordination, balance, running speed and agility, upper-limb coordination and strength. The BOT-2 Brief Form will be administered to subjects who are also completing the KABC-II and takes approximately 20 minutes to complete.

If the subject does not obtain any points in the first two tasks, the motor scales of the BSID-II should be used, even if the subject's cognition was assessed by KABC-II.

5.1.8.5 Children's Communication Checklist, Second Edition (CCC-2)

The CCC-2 is a 70-item questionnaire that was designed to rate aspects of communication in children including speech vocabulary, sentence structure, and social language skills. Within the two domains of language and pragmatics, the following sub-domains are evaluated: speech, syntax, semantics, coherence, initiation, scripted language, context, nonverbal communication, social relations, and interests (Volden 2010, *Am I Speech Lang Pathol*). The CCC-2 takes approximately 5 to 15 minutes to administer to the parent/caregiver and has been validated for use in children between the ages of 4 to 16 years. In this study, the CCC-2 will be administered to parents/caregivers who are assessed by the KABC-II in order to get an estimation of language

Page 64 of 121

and communication development of the subject. Since language development assessment is already part of the BSID-III, the CCC-2 should not be completed by parents/caregivers of the children who are assessed by BSID-III.

5.1.8.6 Children's Sleep Habits Questionnaire, (CSHQ)

The CSHQ is a comprehensive, parent-reported screening survey that has been validated for children aged 4 to 10 years (Owens 2000, *Sleep*); however, it will be completed, if possible, for all subjects treated in the study. The design of the CSHQ is based on common clinical symptom presentations of the most prevalent pediatric diagnoses as described in the *International Classification of Sleep Disorders* (Thorpy 1990, *American Sleep Disorder Association*). The CSHQ takes approximately 20 minutes to complete and consists of 45 questions administered across 8 sleep-wake functions including bedtime resistance, sleep onset delay, sleep duration, sleep anxiety, night awakenings, sleep-disordered breathing, parasomnias, and daytime sleepiness.

5.1.8.7 Sanfilippo Behavior Rating Scale (SBRS)

The SBRS is a parent-reported assessment developed at the University of Minnesota specifically to assess patients with Sanfilippo Syndrome or MPS III disease. The SBRS assesses communication and expression as well as behavior and is administered as 3 sections. The initial assessment includes Section I (Communication), Section II (Temper Tantrums) and Section III (Behavior), which evaluates 15 areas of function that are important for or unique to children with Sanfilippo Syndrome. The 96 questions included in the initial assessment will take approximately 45 minutes to complete. The follow-up assessments that will be completed in Parts B and C include a specific follow-up version of Section I, II and III of the SBRS. This section will assess if there have been any changes since the last visit (increased, stayed the same, decreased). It will take approximately 45 minutes for the parent to complete the 96 questions during the follow-up assessments.

5.1.8.8 12-item Zarit Burden Interview (ZBI)

The 12-item ZBI is a caregiver self-report measure that is used to evaluate levels of stress for caregivers of subjects with Alzheimer's or other forms of dementia. The 12-item ZBI, validated for use in cross-sectional, longitudinal and interventional studies (Bédard 2001, *Gerontologist*), represents a truncated form of the original 22-item ZBI thus enabling easier administration. The assessment takes approximately 5 minutes to complete and measures the caregiver's overall level of burden enabling physicians to identify caregivers who may be at high risk of developing physical and/or emotional problems.

5.1.8.9 10-item Short Form Health Survey for Children (SF-10)

The SF-10 is a parent-completed survey that contains 10 questions adapted from the Child Health Questionnaire and takes less than 5 minutes to complete. The SF-10 has been validated in children aged 5 to 18 years (Zhang 2008, *Health Qual Life Outcomes*); however, it will be completed, if possible, for all subjects treated in the study under the age of 5. The SF-10 provides coverage across a wide range of domains, and is scored to produce physical and psychosocial health summary measures. The survey provides a quick and efficient means to measure health status. Due to its brevity, the SF-10 can be easily integrated and administered within a broader assessment, and is particularly applicable to large-scale child population surveys.

5.2 Clinical Laboratory Assessments

5.2.1 Routine Assessments and Biomarkers

A list of all clinical laboratory tests that will be performed is provided in Table 4; the time points for sample collection are specified in the SOA. Central lab reference ranges will be used throughout the study, including in the event that labs are analyzed locally. All attempts should be made to draw lab samples for central lab analysis when samples are needed for local analysis.

Blood will be collected for standard hematology and serum chemistry (including coagulation parameters).

During Screening, if a subject's ALT or AST is greater than $3 \times ULN$; or a subject has elevated bilirubin or PT/INR, confirmatory testing will be completed. Confirmatory testing may be completed locally or by the central lab, however results will be based on the standardized reference ranges provided in the central laboratory manual for this study. Abnormal safety labs at Screening can be repeated within 1 to 2 weeks. The difference between these two pre-treatment values for each abnormal lab should differ by <20% in each subject.

Efforts should be made by the Investigator to review subject medical history, concomitant medications and health status so that a clear explanation for the elevation is established. The Investigator, in consultation with the Sponsor, shall make a determination of subject eligibility based on review of Exclusion Criteria #8.

During the study, after treatment with SBC-103, in the event that a subject's ALT or AST are $2 \times$ ULN (when baseline ALT or AST were within normal limits) or $3 \times$ ULN (when baseline ALT or AST was greater than $1.5 \times$ ULN), or when a subject has an elevation in bilirubin or PT/INR a confirmatory test should be completed at the earliest possible time point, but not later than the next scheduled visit. Upon positive confirmation of the elevated transaminases as described above, dosing will be paused until AST and ALT have returned to baseline or to study nadir (nadir values may be confirmed by additional lab sampling at the discretion of the investigator, using the same lab for analysis of each sample), or normalized if the baseline level was within normal limits. See Section 6.2.1 for stopping rules.

Every effort will be made to collect urine for urinalysis testing. If urine can be collected, a urine pregnancy test will be performed for females of child-bearing potential. If a urine sample is not able to be provided, a serum pregnancy test will be performed.

Blood will also be collected for determination of NAGLU enzyme activity and NAGLU gene mutation analysis. A sample will be obtained at Screening for measurement of NAGLU enzyme activity by a central laboratory, irrespective of whether historical enzyme activity results are available from a local laboratory. A sample will be collected for determination of NAGLU genotype, only if a historical result is not available from the study central laboratory. If available, historical NAGLU enzyme activity and genotyping data from the local laboratory will also be recorded in the CRF.

Serum, and where possible, urine, will be collected for analysis of MPS IIIB substrate (total HS) and other disease-related exploratory biomarkers including NRE HS derivatives. CSF will be collected via lumbar puncture for analysis of total HS and other disease-related exploratory biomarkers including NRE HS derivatives. All efforts will be made to obtain a blood sample to evaluate serum albumin and serum IgG at the same time as the CSF sample, as reflected in the SOA. The CSF-AI will be calculated as the CSF albumin (mg/mL) / serum albumin (g/L). IgG

index will be calculated as the ([CSF/serum IgG ratio] / [CSF-AI]). Refer to Section 5.2.1.4 for details regarding the lumbar puncture.

A specific sample for exploratory biomarker analysis is being collected in this study; however, remaining blood and urine samples collected in this study may also be used to analyze additional biomarkers of potential clinical interest, if there is sufficient sample and where local regulations permit. As subjects with MPS IIIB may be incontinent, urine samples for routine assessments and biomarkers may not be able to be collected, but should be attempted whenever possible.

Due to the limitations on the volume of blood collection that is considered to be acceptable in young children with very small total circulating blood volumes; see Committee for Medicinal Products for Human Use (CHMP) and Pediatric Committee (PDCO) guidance (EMEA/536810/2008, adopted 25 June 2009), the blood laboratory tests will be ranked by tier. Per individual, the study-related blood loss should not exceed 3% of the total blood volume during a period of four weeks and should not exceed 1% at any single time. The total volume of blood is estimated at 80 to 90 mL/kg body weight; 3% corresponds to about 2.4 to 2.7 mL blood per kg body weight.

Only Tier 1 assessments (see Table 4) are considered mandatory and all efforts should be made to collect these samples in all subjects. Samples for the Tier 2 or Tier 3 assessments will be collected if permitted based on the blood or CSF volume threshold for a subject's weight, as well as the subject's clinical status.

All tests will be performed by a central laboratory with the exception of the urine pregnancy test (or serum pregnancy test if the urine cannot be collected), CSF routine findings, and (as of 23 March 2015) all coagulation panels, which will be done locally.

Clinical laboratory samples will be stored by the Sponsor or designee in a secure and controlled environment until analysis, and will be destroyed by the Sponsor or designee after all worldwide obligations have been met, or sooner if required by local regulations.

Refer to the laboratory manual for further details regarding the collection, processing, and storage of clinical laboratory samples.

Page 67 of 121

Lab Panel	Tier	Matrix	Tests		
Hematology	1	Whole Blood	White blood cell count; red blood cell count; hemoglobin; hematocrit; MCV, MCH, MCHC; platelet count; neutrophil; lymphocytes; monocytes; eosinophils; basophils;		
Serum Chemistry	1	Serum	ALT, AST, alkaline phosphatase, GGT, albumin, total bilirubin, serum electrolytes (sodium, potassium, chloride, calcium, magnesium, phosphorus), glucose, creatinine, bicarbonate, total protein, BUN		
Coagulation	1	Plasma ^c	PT, INR ^c		
Urinalysis	N/A	Urine	pH, clarity, color, specific gravity, glucose, ketones, blood, protein, nitrite, and leukocytes (microscopic examination will only be done if urinalysis is positive for blood, nitrite, or leukocytes, or if protein is $>1+$)		
Pregnancy test ^a	N/A	Urine			
MPS IIIB	1	Dried blood spot	NAGLU enzyme activity		
Diagnostics	1	Dried blood spot	NAGLU gene mutation analysis		
РК	1	Serum	PK profile		
РК	3	CSF	SBC-103 concentration		
ADA	1	Serum	Anti-SBC-103 Antibody (IgM, IgG and IgE). Subjects who experience a moderate or severe IAR should have a serum sample collected for ADA during the next study visit (\geq 4 days after the IAR) prior to the infusion.		
Biomarkers	1	Serum	HS (total and NRE)		
	2	Serum	Ferritin and chitotriosidase		
	2	Plasma	Glutamic acid and glycine		
	2	Serum	IgG, inflammatory markers, and exploratory biomarkers		
	N/A	Urine	HS (total and NRE)		
	1	CSF	HS (total and NRE)		
	2	CSF	HGF, calbindin D, Tau, pTau, amyloid β , albumin, IgG, glutamic acid and glycine		
	1	CSF/Serum ^b	CSF/Serum Albumin Index (CSF-AI) and IgG index ([CSF/serum IgG ratio] / [CSF-AI])		
	2	CSF ^c	Routine findings (cell counts, glucose, protein) ^c		
DNA Sample ^d	2	Whole blood			
Serum Tryptase	If clinically indicated	Serum	Subjects who experience a moderate or severe IAR should have a serum sample collected for analysis of tryptase 1-3 hours after the IAR onset and another serum sample for tryptase and ADA during the next study visit (\geq 4 days after the IAR) prior to the infusion.		

Table 4:	Clinical Laboratory Tests
----------	----------------------------------

Key: ADA = anti-drug antibodies; ALT = alanine aminotransferase; AST = aspartate aminotransferase; BUN = blood urea nitrogen; CSF = cerebrospinal fluid; DNA = deoxyribonucleic acid; GGT = gamma-glutamyl transpeptidase; HGF = hepatocyte growth factor; HS = heparan sulfate; IAR = infusion-associated reaction; IgE = immunoglobulin E; IgG = immunoglobulin G; IgG index = immunoglobulin G index; IgM = immunoglobulin M; INR= international normalized ratio; MCH = mean corpuscular hemoglobin; MCHC = mean corpuscular hemoglobin concentration; MCV = mean corpuscular volume; N/A = not applicable; NRE = non-reducing end; NAGLU = alpha-N-acetylglucosaminidase; PK = pharmacokinetics; PT = prothrombin time.

Unless specified in the SOA, the laboratory tests apply to Part A (Initial Therapy), Part B (Therapy at 1 and/or 3 mg/kg), and Part C (Therapy at 5 and/or 10 mg/kg).

^a Test performed by a local laboratory for all female subjects of child-bearing potential. If a urine sample is not able to be provided, a serum pregnancy test will be performed by a local laboratory.

^b Ensure that serum albumin is collected at each time point a CSF sample is collected. If a serum chemistry is not scheduled at the same study visit, a serum albumin should be drawn.

- ^c Test performed by a local laboratory.
- ^d Performed only where local regulations permit and consent is received from the subject or the subject's parent or legal guardian.

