6.2 Stopping Rules

6.2.1 Stopping Rules in Individual Subjects

During Part A (Initial Therapy), Part B (Therapy at 1 and/or 3 mg/kg), and Part C (Therapy at 5 and/or 10 mg/kg), subjects who experience a severe IAR, a serious or severe AE that is

Page 75 of 121

considered related to SBC-103, or a significant elevation in specific laboratory values will have SBC-103 dosing paused based on the rules described below.

For IARs:

- Subjects who develop a severe IAR, as defined in Section 7.1.3, must stop treatment until their information is reviewed by the SRC. Dosing with alterations to the infusion regimen (eg, pretreatment or slowing the rate of infusion) may resume once the SRC and the Sponsor approve.
- Subjects with mild or moderate IARs can continue receiving SBC-103 in the study. The SRC or Sponsor may recommend alterations to the infusion regimen (eg, pretreatment or slowing the rate of infusion).

For all other AEs (ie, AEs that are not characterized as IARs):

- Any event considered related to SBC-103 which is either serious or severe will result in pausing additional dosing in an individual subject. The SRC and the Sponsor will review the data and will resume dosing only after review and agreement.
- Subjects with mild or moderate non-serious AEs can continue receiving SBC-103 in the study.

For Laboratory Values:

- Dosing will be paused based on confirmed elevations in AST or ALT under the following circumstances:
 - In the event that a subject's AST or ALT is greater than or equal to 2 times the ULN (when baseline ALT or AST was within normal limits)
 - In the event that a subject's AST or ALT is greater than or equal to 3 times the ULN (if baseline ALT or AST greater than 1.5 ULN).

Dosing will only resume after AST or ALT have returned to baseline or to study nadir (nadir values may be confirmed by additional lab sampling at the discretion of the investigator, using the same lab for analysis of each sample), or normalized if the baseline level was within normal limits.

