The subject should be restarted at a reduced dose. For example, if a subject was receiving a dose of 10 mg/kg, he/she would be restarted at 5 mg/kg; subjects receiving 5 mg/kg would be restarted at 3 mg/kg; etc. In the event that the subject was receiving a dose of 0.3mg/kg, he/she may resume at the 0.3 mg/kg dose only after AST or ALT have returned at least to baseline or to study nadir (nadir values may be confirmed by additional lab sampling at the discretion of the investigator, using the same lab for analysis of each sample), or normalized if the baseline level was within normal limits.

If after resuming treatment at the lower dose, the ALT or AST elevation recurs at greater than or equal to 2 times the ULN (for those with ALT or AST within normal limits at baseline) or 2 times the baseline value (for those with abnormal ALT or AST at baseline) study drug should be stopped and not resumed. Dosing will be paused based on confirmed elevations in AST or ALT with accompanying elevations in the following

• Confirmed bilirubin greater than 1.5 times ULN

- Confirmed INR increase of 0.2
- Eosinophilia (more than 5%), rash or fever

If these bilirubin and INR values normalize (and the independent SRC believes that it is safe to do so), the subject may resume dosing on a lower dose of the study drug (eg, those on a 3 mg/kg would resume dosing at 1 mg/kg, those on a 0.3 mg/kg dose would resume the 0.3 mg/kg dose). However, in this scenario, if a subject develops recurrent elevations in AST or ALT (with or without elevations in total bilirubin or INR), the drug should be stopped and not resumed.

Subjects whose rise in LFTs is accompanied by eosinophilia (more than 5%), rash or fever should not be restarted on the study drug.

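### The ALT/AST dosing pause waits for a confirmed value, the repeat may run to the next (almost always infusion) visit, and nothing makes that infusion wait for the result

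*Protocol*

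**What the plan says.** The on-treatment paragraph of Protocol Section 5.2.1 sets the trigger for a repeat at 2 times the upper limit of normal (baseline within normal limits) or 3 times (baseline above 1.5 times). The repeat then has two time conditions: "a confirmatory test should be completed at the earliest possible time point, but not later than the next scheduled visit". The consequence follows: "Upon positive confirmation of the elevated transaminases as described above, dosing will be paused". Section 6.2.1 is worded the same way: "Dosing will be paused based on confirmed elevations in AST or ALT under the following circumstances".

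After a confirmed elevation, dosing stops until the values recover and then resumes one level down. In Part C a child on "10 mg/kg, he/she would be restarted at 5 mg/kg; subjects receiving 5 mg/kg would be restarted at 3 mg/kg".

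On where the sample is analyzed, Section 5.2.1 states that "All tests will be performed by a central laboratory with the exception of the urine pregnancy test", routine CSF findings and coagulation panels. Chemistry is not among the exceptions. Local analysis is nevertheless foreseen. The Screening paragraph says "Confirmatory testing may be completed locally or by the central lab", and a general sentence adds: "All attempts should be made to draw lab samples for central lab analysis when samples are needed for local analysis". No turnaround time is given for either route.

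**The concern.** A pause rule protects a child only if the information that triggers it arrives before the next dose. Here the rule acts on the second value, and the outer limit for that value is a visit at which the child is normally infused. The text does not say which comes first on that day, the result or the infusion. A child whose first value already meets the threshold can therefore receive one more full dose without any departure from the written rule.

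Safety and tolerability are the primary objective, the children are enrolled at 2 to under 12 years, and Section 1.5.2 names monitoring of liver parameters as a safeguard, pointing to Sections 5.2 and 6.2. The order of result and infusion is therefore worth stating.

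**Working it through.** No sample-size or power figure is involved. The check is a reading of the rule, a count of visits, and a count of infusions.

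**1. Is the next scheduled visit an infusion visit?** For each scheduled chemistry draw after the first dose (Protocol Appendices A to D, with the clearer copies in SAP Section 9.1), I looked at the visit that follows.

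| Period | Chemistry draws | Next visit carries an infusion | Exception |
|---|---|---|---|
| Part A (Day 1, Weeks 4 to 24) | 7 | 6 | Week 24, followed by Week 26 off therapy |
| Part B, Weeks 28 to 52 | 4 | 4 | none |
| Part B, Years 2 and 3 | 12 | 11 | Week 156, followed by Week 160 follow-up |
| Part C, Day 0C to Week 120C | 18 | 18 | none* |
| Total | 7 + 4 + 12 + 18 = 41 | 6 + 4 + 11 + 18 = 39 | |

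39/41 = 95%. *The first subject at each Part C dose also has a Day 1C visit without infusion. The Part C count leaves out the last column (Week 130C) and the end-of-treatment visit. These are entries in the schedule, not one child's visits: no child passes through every Part B and Part C column.

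**2. How far away is that visit?** Under every-other-week dosing it is nominally 14 days after a draw taken at an infusion visit. The minimum is 10 days (stated minimum spacing), and the maximum from the ±5-day windows is 14 + 5 + 5 = 24 days.

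**3. How many infusions are at issue?** Take an elevated pre-dose sample at infusion visit *t*. The infusion at *t* is normally given before that result is known; it is not counted here.

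- Latest path, repeat result not known before dosing at the next visit: infusions at *t* and *t* + 2 weeks, and the pause first acts at *t* + 4 weeks. That is 2 infusions after the elevated draw.
- Same path with a hold until the result is read: 1 infusion, at *t*.
- Difference: 2 − 1 = 1.

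The infusion after that is at least 10 days later, so a second is not at issue if the result is back within that time. If the repeat result is read before the next visit, the difference is 0.

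**4. Does the meaning of *completed* matter?** The Screening sentence uses the word of testing done at a laboratory, which suggests a test that has been analyzed. On that reading the result must exist by the next visit, and only the order within that day is open. If the word means drawn, the result may also come back after that day. Either way, the exposed infusion is the one at that visit.

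**5. Does another sentence close the gap?**

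- The pre-dose mark in the schedules fixes when a scheduled sample is taken, not when its result is read.
- Section 7.2.4 asks for an immediate repeat of unexplained, clinically significant values. It refers back to 5.2.1 and 6.2.1 for the pause and says nothing about the next infusion.
- The Synopsis and Section 6.2.2 let the safety committee or Sponsor request a pause, and Section 6.1.1 allows one for poor tolerability. All are discretionary. The mandatory part of 6.2.2 needs serious, severe or life-threatening related events.
- The adverse-event rule in 6.2.1 reads "Any event considered related to SBC-103 which is either serious or severe will result in pausing additional dosing in an individual subject". Under Section 7.1.2 a laboratory value is not an adverse event unless the investigator judges it clinically significant.
- SAP Section 7.3.3.1 only lists laboratory data.

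By contrast, Section 5.2.1.4 requires coagulation results before sedation or lumbar puncture, and Section 6.1 requires safety laboratory tests before dosing resumes after 3 or more consecutive missed infusions in Part B. The protocol states a results-first order where it wants one.

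**The case against.** The best defence is that the text already pushes toward an early repeat. Section 5.2.1 first asks for the earliest possible time, so a site that could repeat sooner but waits for the last permitted day is not following it. A reader might infer that waiting and repeating promptly are equally compliant; the documents do not support that. The gap is confined to cases where the visit really is the earliest feasible time, or where the result is not back before dosing. If *completed* means analyzed, a central repeat without a same-day result would have to be drawn before the visit, and the result would usually be known in time. This narrows the point considerably.

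Section 7.2.4 is the closest counter-text. Its cross-reference to the transaminase pausing rules suggests that values at the pause level were meant to be repeated at once. That shortens the likely delay, but it is limited to unexplained, clinically significant values and does not make the infusion wait.

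Turnaround and alert procedures may be in the laboratory manual, so the protocol's silence is weak evidence about practice. Requiring confirmation before a formal pause is also a reasonable, deliberate choice, and it is not in question here.

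Finally, a reader might note that 10 mg/kg is twice the 5 mg/kg restart dose and read this as a doubling of risk. It is not: the extra infusion is at the child's assigned, unchanged dose, and the ratio measures neither excess exposure against plan nor hepatic risk.

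**Conclusion.** The point holds as a gap in sequencing. The pause needs a confirmed value, the outer limit for the repeat is a visit that is almost always an infusion visit, and no sentence holds that infusion for the result. Its size is normally at most one further full-dose infusion per episode, and zero when the repeat result is read first.

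This assumes that the result is back within the 10-day minimum before the following infusion, and that the unseen laboratory manual and safety committee charter do not already impose a hold. Frequency cannot be estimated, and the documents do not show that such an infusion was given. A careful investigator may well wait; the text does not require it. I would raise it as a change to consider, with medium confidence.

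**What to change.** In Protocol Section 5.2.1, directly after the clause that sets the next scheduled visit as the limit, and in Section 6.2.1 under the laboratory-values heading, add: *where ALT or AST was the trigger, the next infusion will not be given until the repeat ALT/AST result has been reviewed.*

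In the on-treatment paragraph of 5.2.1, state that this repeat may be analyzed locally against the central reference ranges. Leave the list of tests that must be done locally as it is, apart from a cross-reference to this exception; adding ALT/AST repeats to that list would make local testing compulsory. Thresholds, and the confirmation requirement for a formal pause and dose reduction, stay unchanged.

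The cost is an occasional infusion delayed after a first value that is not confirmed, for a time that depends on laboratory turnaround. A local repeat may add a small blood sample, which must fit within the 1% single-draw and 3% four-week limits. SAP Section 4 records that the development program was stopped in July 2017, so the practical use of the change now is in any protocol that reuses this rule.
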